8.1.6 Follow-up visit (Day 54±2, Week 9)

During this visit, this investigator or designee will:

1. Ask the subject about AEs by asking an open-ended question taking care not to influence the subject's answer, such as "Have you noticed any change in your health since the last visit?" Record all events, as appropriate on the corresponding eCRF pages;

2. Ask the Subject whether there have been any changes to his/her concomitant therapies/procedures (added, removed, or changed) since the previous visit. Document all changes on the Drugs/Therapies and/or Medical/Surgical Procedures form of the eCRF;
3. Complete pregnancy test if the subject is a female of childbearing potential.
4. Perform a physical examination of the subject, including neurological examination and vital signs (blood pressure, pulse rate);
5. Check the good healing of the biopsies (if applicable).
6. Remove the suture (if applicable).
7. Complete the exit form

8.1.7 Unscheduled Visit

In the event the subject has to come back to the center for an unscheduled visit, due to an increase in the BSA (see section 6.4.3), the procedures described hereunder will have to be performed.

During this visit, this investigator or designee will:

1. Ask the subject about AEs by asking an open-ended question taking care not to influence the subject's answer, such as "Have you noticed any change in your health since the last visit?" Record all events, as appropriate on the corresponding eCRF pages;
2. Ask the Subject whether there have been any changes to his/her concomitant therapies/procedures (added, removed, or changed) since the previous visit. Document all changes on the Drugs/Therapies and/or Medical/Surgical Procedures form of the eCRF;
3. Assess the BSA.
4. Select and identify a target plaque that is representative of the increasing of the disease of the subject and take standardized photo of this target plaque
5. Define whether the treatment is maintained, up to 8 FTUs, or discontinued
6. EASI Score : Assess the area score and the severity score of each body region
7. Remind the subject for the next visit date.

8.2 Subject instructions (other than study drug(s) administration)

Throughout the study duration, subjects should be instructed to avoid concomitant use of other potentially irritating topical products such as medicated or abrasive soaps & cleansers, soaps and cosmetics that have strong skin-drying effect and products with high concentration of alcohol, astringents, spices or limes.

Exposure to sunlight, including sunlamps, should be avoided during the study duration. The use of a protective apparel is recommended when exposure cannot be avoided. Sunscreens may be used when sun exposure is unavoidable.

The subjects should also be instructed to not participate to another clinical trial of a drug or device within one month after the last visit.

All subjects will have to use their own emollient throughout the study duration once a day in the morning on AD lesions, including during the screening period. For those subjects who do not have an emollient, they will be prescribed one.

9 STATISTICAL METHODS PLANNED

9.1 Statistical and analytical plans

A statistical analysis plan (SAP) will be developed and issued as a separate document. The SAP will contain a more detailed and technical description of specific data conventions, calculations and of statistical procedures for executing the analysis strategies that are specified in the sections of the clinical trial outline below. Changes to CCI [REDACTED] or other non-confirmatory analyses made after the SAP has been finalized, along with an explanation as to when and why they occurred, will be documented in the clinical study report. Post hoc exploratory analyses will also be clearly identified in the Clinical Study Report (CSR).

Any change made to the finalized SAP will be documented in the clinical trial report.

9.1.1 Data transformations

C_t , cumulated concentration in the SC, concentration in the skin biopsy (epidermis and dermis), and cumulated concentration in the total skin will be log transformed before any analysis.

9.1.2 Populations analyzed and evaluability

The statistical analyses will be performed based on the following subject populations:

9.1.2.1 *Intent-to-treat (ITT) Efficacy analysis set*

The ITT set is defined as any subjects who are randomized. Data from subjects included in the ITT population will be analyzed according to the treatment as randomized.

9.1.2.2 *Per-protocol (PP) Efficacy analysis set*

Per Protocol (PP) set is defined as the ITT population, after exclusion of subjects deemed non-evaluable for efficacy due to major deviations from the protocol. Major deviations are categorized into 4 categories:

- Entrance criteria deviations,
- Non compliance,
- Concomitant therapies taken during the study and/or Concomitant illnesses, interfering with efficacy,
- Administrative errors such as unblinding or study drug dispensing errors.

Major deviations will be identified and categorized before database lock and unblinding, during a blind data review meeting.

9.1.2.3 *Safety Analysis set*

The Safety set is defined as comprising the ITT Population subjects who applied/were administered the study drug(s) at least once. In practice, only the subjects who return their study drug(s) unopened will be excluded from the Safety Population. All safety data will be summarized based on the Safety Population.

9.1.3 *Data presentation and graphics*

For statistical analyses purpose, baseline is defined as the last measurement prior to the first application of the study drug.

A type I error of 0.05 (two-sided test) will be used to declare statistical significance.

The subject disposition, demographics, Baseline characteristics, previous therapies/procedures, concomitant therapies/procedures will be summarized by descriptive statistics based on the ITT population. Treatment duration and compliance data will be summarized based on the Safety Population.

For statistical analysis purposes, previous therapies/procedures are defined as those ending at Baseline or before; and concomitant therapies/procedures are defined as those ongoing at the Baseline visit or starting after the Baseline visit.

All efficacy variables will be summarized by treatment at each visit. The categorical variables (e.g. IGA), and their changes from Baseline will be summarized by frequency and percentage for each response category (N, %). The continuous variables (EASI, objective SCORAD, TSS, and their percent changes, Pruritus (weekly average NRS), VRS and their changes from baseline)

will be summarized using means, medians, Q1, Q3, minimum, maximum, and standard deviations.

Treatment-emergent Adverse Events (TEAEs) are defined as AEs with onset on or after first dose of study drug; or those AEs with onset prior to first dose of study drug but worsened during treatment.

TEAEs will be tabulated in frequency tables by System Organ Class (SOC) and Preferred Term (PT) based on the Medical Dictionary for Regulatory Activities (MedDRA). Additional summary tables will be provided for SAEs, AEs considered related to the study drug, severe AEs, AESIs and AEs leading to discontinuation. For a given AE, a subject will be counted once even if he/she has experienced multiple episodes of that particular AE. In addition, non TEAEs will be summarized or listed separately.

Descriptive statistics for each laboratory parameter at Screening and any time points and shift table for laboratory parameters at Screening versus end of study will be provided.

Vital signs and physical examinations will be descriptively summarized.

Plasma concentration, Skin parameter concentration, as well the Skin/plasma ratio will be descriptively summarized

Subgroup analyses will be explored by IgE on the primary endpoint.

9.1.3.1 *Analysis of the primary efficacy endpoint*

The Primary efficacy endpoint, EASI score least square mean percent change from baseline at week 6, will be analyzed via an analysis of variance with the Treatment group as factor and Center as a cofactor.

9.1.3.2 *Analysis of the Secondary Efficacy Endpoint*

EASI score least square mean percent change from baseline at any other evaluation visit, will be analyzed via an analysis of variance with the Treatment group as factor and Center as a cofactor.

Objective SCORAD and TSS least square mean percent change from baseline at each evaluation visit, will be analyzed individually via an analysis of variance with including the Treatment group as factor and Center as a cofactor.

Proportion of subjects achieving success (IGA=0[clear] or IGA=1[Almost clear]) will be analyzed at each evaluation visit using the Cochran-Mantel-Haenszel (CMH) test stratified by center with the ridit transformation and the general association statistic (FREQ procedure from SAS).

Change in Pruritus (Weekly average NRS) will be analyzed at each evaluation visit by the CMH test stratified by analysis center with the ridit transformation and the row mean difference statistic (FREQ procedure from SAS).

9.1.3.3 *Imputation of missing data*

For the primary endpoint several sensitivity analyses will be conducted:

- The primary imputation method will use the LOCF (Last observation carried forward) approach.
- For sensitivity purpose method of imputation for missing data will be MI (Multiple Imputation) using the Missing At Random (MAR) assumption. The MI procedure of the SAS system will be used to generate five sets of data with missing values imputed from observed data. It is expected that the pattern of missing data will be monotonic, with slight deviations being corrected by the Markov Chain Monte Carlo (MCMC) method of the MI procedure. Linear regression will be employed to model the missing EASI score, with the following covariates included in the imputation model: treatment and non-missing data from earlier timepoints. The imputed datasets will be analyzed using the methodology described for percent change from baseline in EASI score. The results from the analysis of the multiple imputed datasets will be combined by the MIANALYZE procedure of the SAS system. The seed number to be used will be the protocol number (109696).

For secondary endpoints:

- The primary imputation method will use the LOCF (Last observation carried forward) approach.

In addition, all analyses for primary and secondary endpoints will be conducted on the Per Protocol set.

9.1.3.4 *Handling of Multiplicity*

The primary purpose is to compare CD5024 cream 0.3% QD daily to its vehicle in terms of EASI score. P-values for secondary criteria will be given for indicative purposes so no adjustment will be made. All tests will be two-sided and significance will be declared at a 5% two-sided level.

CCI

CCI

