Clinical Trial Title: Safety and efficacy of CD5024 0.3% cream in subjects with atopic dermatitis	
	period from a previous clinical trial of a drug or device (Screening visit)
Investigational product	
INN Name	Ivermectin
Internal code	CD5024
Pharmaceutical form	Cream
Strength	0.3%
Dosage (total daily dose)	Up to 4 g daily (depending on the tBSA and BSA)
Route	Topical
Duration of administration	6 weeks
Dose regimen	Once a day, 7 days a week for 6 weeks (42 applications)
Location of treated area	All body areas (except scalp & genitals)
Comparator	
INN Name	NA
Internal code	CD5024 Placebo
Pharmaceutical form:	Cream
Dosage (total daily dose)	Up to 4 g daily (depending on the tBSA and BSA)
Route	Topical
Duration of administration	6 weeks
Dose regimen	Once a day, 7 days a week for 6 weeks (42 applications)
Location of treated area	All body areas (except scalp & genitals)
Efficacy assessments	Clinical evaluation of IGA, BSA, TSS, Modified Objective SCORAD and EASI by the Investigator. Patient-reported Outcomes : NRS and VRS (Pruritus assessment)
Efficacy endpoints	Primary efficacy endpoints: The Primary efficacy endpoint is the EASI percent change from baseline at Week 6. Secondary efficacy endpoints: 
 ■ The EASI percent change from baseline at each other evaluation visit and change from Baseline in EASI at each evaluation visit. ■ Investigator Global Assessment in terms of distribution and in terms of success rate (Success is defined as a subject with an IGA score of 0 (clear) or 1 (Almost clear) at each evaluation visit. ■ Percent Change from baseline of the TSS of the target plaque ■ Percent Change from baseline of the Modified Objective SCORAD ■ Pruritus (NRS, VRS) and their changes from Baseline at each evaluation visit.
Safety assessment:	
 ■ Adverse events ■ Laboratory blood tests ■ Vital signs and physical examination

Clinical Trial Title: Safety and efficacy of CD5024 0.3% cream in subjects with atopic dermatitis	
Safety endpoints:	
■ ECG■ Incidence and multiplicity of adverse events■ Laboratory blood hematology and blood chemistry■ Vital signs and physical examination
CCI	
Principal statistical method:	The Primary efficacy endpoint, EASI score least square mean percent change from baseline at week 6, will be analyzed via an analysis of variance with the Treatment group as factor and Center as a cofactor.

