7.1.6 Eczema Area and Severity Index (EASI)

The EASI score is a tool used to measure the extent (area) and severity of atopic eczema (Eczema Area and Severity Index). The EASI score will be calculated directly in the e-CRF on Day 1, Day 8, Day 15, Day 22, Day 29, Day 36, and Day 43 or earlier in case of early termination and at the unscheduled visit if applicable. The investigator or designee will have to fill in, for each of the four body regions listed below, the area score and the severity score needed for EASI score calculation.

7.1.6.1 *The four body regions*

Head and Neck, Trunk, Upper limbs, Lower limbs (including buttocks).

7.1.6.2 *The area score (A)*

The area score will be recorded for each body region, as the percentage of skin affected by atopic dermatitis for this region. The area score is defined in the Table 7 below.

Table 7 Area Score for EASI calculation

Area Score	Percentage of skin affected in this region
0	No eczema
1	1% to <10% affected
2	10% to <30% affected
3	30% to <50% affected
4	50% to <70% affected
5	70% to <90% affected
6	90% to 100% affected

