7.1.8 Efficacy endpoints

Primary efficacy endpoint:

The Primary efficacy endpoint is the EASI percent change from baseline at Week 6.

Secondary efficacy endpoints:

- The EASI percent change from baseline at each other evaluation visit and change from Baseline in EASI at each evaluation visit.
- Investigator Global Assessment in terms of distribution and in terms of success rate (Success is defined as a subject with an IGA score of 0 (clear) or 1 (Almost clear) at each evaluation visit.
- Percent Change from baseline of the TSS of the target plaque
- Percent Change from baseline of the Modified Objective SCORAD
- Pruritus (NRS, VRS) and their changes from Baseline at each evaluation visit.

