8.1.2 Baseline visit (Day 1, Week 1)

At the Baseline visit, the Investigator or designee will:

1. Ask the subject about AEs by asking an open-ended question taking care not to influence the subject's answer, such as "Have you noticed any change in your health since the last visit?" Record all events, as appropriate on the corresponding eCRF pages;
2. Ask the Subject whether there have been any changes to his/her concomitant therapies/procedures (added, removed, or changed) since the previous visit. Document all changes on the Drugs/Therapies and/or Medical/Surgical Procedures form of the eCRF;
3. Check laboratory results from the Screening visit.
4. Complete pregnancy test if the subject is a female of childbearing potential.
5. Perform a physical examination of the subject, including neurological examination and vital signs (blood pressure, pulse rate);
6. Perform an ECG.
7. Confirm subject meets inclusion/non-inclusion criteria.
8. Assess the BSA.
9. Assess IGA score (and hand IGA if applicable).
10. Select and identify a target plaque that is representative of the overall disease of the subject and take standardized photo of this target plaque
11. Assess the TSS and the modified-objective SCORAD :
 - a. Assess the individual clinical scores of the target plaque
 - b. Assess skin dryness scored on a non-treated area
12. EASI Score : Assess the area score and the severity score of each body region
13. Assign a randomization number.
14. Weigh the study products to be provided to the subject and record the weights
15. Dispense study product and provide written/oral instructions for study drug application/administration.

16. A member of the staff other than the Investigator will explain the subject how to apply the study product and will supervise the subject while applying the appropriate quantity of study products on targeted areas.
17. Instruct subject to complete the application diary for the coming applications at home on a daily basis.
18. Ask the subject to evaluate its pruritus severity using the NRS twice daily, every day until the next visit and to collect the data on the dedicated diary, to be taken with him to the center at each study visit.
19. Ask the subject to evaluate its pruritus severity over the past 24h, using the VRS and to collect the data on the dedicated diary, to be taken with him to the center at each study visit.
20. Complete the Subject Enrollment Log.
21. Remind the subject for the next visit date.

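### The primary EASI model, an ANOVA on treatment and centre, is valid but omits the baseline EASI already collected, forgoing likely precision and any correction for chance baseline imbalance

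*Protocol*

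**What the plan says.** The endpoint is defined in section 7.1.8: "The Primary efficacy endpoint is the EASI percent change from baseline at Week 6". Section 9.1.3.1 states that it "will be analyzed via an analysis of variance with the Treatment group as factor and Center as a cofactor", and the synopsis row on the principal statistical method gives the same model.

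Section 9.1.3.2 uses treatment and centre again for EASI percent change at the other visits. It does the same for two further scores: "Objective SCORAD and TSS least square mean percent change from baseline at each evaluation visit, will be analyzed individually via an analysis of variance".

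Baseline EASI is available. Section 8.1.2 lists, at Day 1, "EASI Score : Assess the area score and the severity score of each body region" (step 12), immediately before the randomization number is assigned (step 13).

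Earlier EASI values enter a model in one place only, the multiple-imputation sensitivity analysis in section 9.1.3.3: "the following covariates included in the imputation model: treatment and non-missing data from earlier timepoints". The completed datasets are then analysed with the method already described for percent change, that is, without baseline.

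**The concern.** If percent change in EASI depends on where a subject starts, the ANOVA leaves that variation in the residual, which widens the interval and lowers power. Dividing by baseline does not settle the matter. It removes the dependence only if response is exactly proportional to baseline, and regression to the mean can leave percent change correlated with the starting value.

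The second issue is chance imbalance. The protocol describes 1:1 allocation from a list and states no stratification by baseline EASI, so two arms of about 30 can differ in mean baseline. Over repeated trials the ANOVA estimate is unbiased and its interval allows for this. In the single trial that is run, the observed difference stays in the estimate to the extent that r is not zero. Adding the covariate after seeing an imbalance would be post hoc.

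The stakes are moderate. The study is exploratory, its primary objective is safety, and p-values for secondary criteria are indicative. The sample size is nevertheless built on EASI, and significance is declared on it at 5% two-sided.

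**Working it through.** **Inputs from the protocol.** Difference 30 points and SD 40 (9.2.2); 30 randomized per arm, 1:1, 80% power (9.2.3); two-sided alpha 0.05 (section 9.1.3); about 5 centres (section 3).

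**Assumption.** The within-arm correlation r between baseline EASI and percent change is not in the protocol. The range 0 to 0.5 is assumed.

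**Step 1: the plan's own figure.** SE = 40 × sqrt(2/30) = 10.33. With treatment and 5 centres the error df are 60 − 6 = 54. The noncentrality is 30/10.33 = 2.90, and noncentral t power is 0.814. The stated 80% reproduces.

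**Step 2: baseline added.** Error df fall to 53. The residual SD becomes 40 × sqrt(1 − r²), and estimating the covariate slope multiplies the variance by 1 + 1/52:

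SE = 40 × sqrt(1 − r²) × sqrt((2/30) × (1 + 1/52))

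| r | SE | Power | Change from 0.814 |
|---|---|---|---|
| 0 | 10.43 | 0.806 | −0.008 |
| 0.1 | 10.37 | 0.810 | −0.004 |
| 0.14 | 10.32 | 0.814 | 0 |
| 0.2 | 10.22 | 0.822 | +0.008 |
| 0.3 | 9.95 | 0.842 | +0.028 |
| 0.5 | 9.03 | 0.903 | +0.089 |

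**Step 3: the gain in subjects.** Equivalent n per arm = 30 / ((1 − r²)(1 + 1/52)). This is 30.7, 32.3 and 39.2 at r = 0.2, 0.3 and 0.5, or about 0.7, 2.3 and 9.2 extra subjects per arm.

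**Step 4: chance imbalance.** The arm difference in mean baseline has a standard error of sqrt(2/30) = 0.258 baseline SDs. It exceeds 0.25 SD in about 33% of trials and 0.5 SD in about 5%. The unadjusted estimate shifts by r × 40 × imbalance:

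| Imbalance | r = 0.2 | r = 0.3 | r = 0.5 |
|---|---|---|---|
| 0.258 SD (one SE) | 2.1 | 3.1 | 5.2 |
| 0.5 SD | 4 | 6 | 10 |

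These shifts are in percentage points, against a target of 30 and a standard error of 10.3.

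**Step 5: simulation.** Normal data, 5 centres of 12. In 40,000 trials per r, ANOVA power was 0.813 to 0.816 throughout; ANCOVA power was 0.805, 0.820, 0.841 and 0.905 at r = 0, 0.2, 0.3 and 0.5. In a separate run of 8,000 trials per setting, ANOVA type I error was 0.048 to 0.049.

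**Step 6: the larger SD.** Section 9.2.1 reports SD 45 in the sponsor's own vehicle trial. At that SD the ANOVA has power 0.718; with baseline it is 0.709, 0.749 and 0.826 at r = 0, 0.3 and 0.5.

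**The case against.** The strongest reply is that nothing here is an error. The ANOVA is valid, the synopsis and section 9.1.3.1 agree, and the stated power reproduces. The benefit rests on a correlation that the protocol does not report. It may be small, because entry is limited to IGA 3 and BSA 1% to 8% (section 5.2.1) and the EASI area score is banded (Table 7). Below r = 0.14 there is a slight loss, and at r = 0.2 the gain is under one subject per arm. At r = 0.2 to 0.3, a one-standard-error imbalance moves the estimate by at most about 0.3 standard errors.

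Much of this stands. It limits the size of the point and means the gain can only be called likely. It does not make r negligible. With regional severity 8 and area score 1, Table 9 gives 8 × 1 × 0.2 = 1.6 for the upper limbs alone and 8 × 1 × (0.1 + 0.3 + 0.2 + 0.4) = 8.0 for all four regions. Baseline EASI can therefore vary five-fold at the same severity.

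A further objection is that the small cost is shown only for normal, equal-variance data, whereas small baseline values can make percent change unstable. A rough simulation with skewed baselines and small denominators also lost no more than about one power point when r was near zero.

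Finally, the model is not detail awaiting the SAP. The protocol states it in two places, so a SAP that added baseline would depart from the stated primary analysis.

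**Conclusion.** The concern holds. The protocol fixes a valid but less efficient primary model and leaves out a prognostic value that it already collects. Type I error and the sample size statement are not in question.

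The likely effect runs from a loss of 0.8 power points at r = 0 to gains of about 3 points at r = 0.3 and 9 at r = 0.5. This assumes SD 40, a 30-point difference, 30 per arm and 5 centres. The correlation is an assumption, and the entry criteria may keep it low. The trade is asymmetric in favour of adjusting. No magnitude was computed for TSS or objective SCORAD. The change should be made, but an exploratory Phase IIa trial does not depend on it.

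**What to change.** Before unblinding, amend the synopsis and sections 9.1.3.1 and 9.1.3.2:

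- For EASI percent change at Week 6 and at the other visits, specify an ANCOVA with treatment and centre as factors and baseline EASI as a continuous covariate.
- For TSS and objective SCORAD, use the matching baseline score in the same way.
- In section 9.1.3.3, analyse the multiply imputed datasets with this model.
- Keep the present ANOVA as a sensitivity analysis.

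The cost is one degree of freedom and no new data, with a loss of at most about one power point if r is near zero. The covariate deals only with dependence of the mean on baseline. It does not address skew or unequal variance of percent change.
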